12.5 Not evaluable (NE)

When no imaging/measurement is done at all at a particular time point, the patient is considered not evaluable (NE) at that time point.

12.6 Early death

If the patient has no repeat tumor assessments following initiation of study therapy resulting from the death of the patient due to disease or treatment, it is considered early death.

12.7 Symptomatic Deterioration

Patients with global deterioration of health status requiring discontinuation of treatment without objective evidence of disease progression at that time be recorded as "symptomatic deterioration". Every effort should be made to document objective progression even after discontinuation of treatment.

12.8 Duration of response

Defined as the time measurement criteria are first met for CR/PR until the first date that recurrent or progressive disease is objectively documented (taking as reference for progressive disease the smallest measurement recorded on study).

12.9 Duration of stable disease

Measured from the start of the treatment until the criteria for progression are met, taking as reference the smallest sum on study (if the baseline sum is the smallest, this is the reference for calculation of PD).

12.10 Progression-Free Survival (PFS)

PFS is defined as the period from start of study treatment until recurrent or progressive of disease (POD) is objectively documented (taking as reference for progressive disease the smallest measurement recorded on study), death, or date of last evaluable tumor assessment

12.11 Overall Survival (OS)

OS is defined as the observed length of life from start of study treatment to death or the date of last contact.

12.12 Secondary Response Criteria – Modified immune-related response evaluation Criteria in Solid (irRECIST)

Immune related RECIST (irRECIST)

In 2013, Nishino et al. demonstrated that immune-related response criteria using unidimensional measurements were highly concordant with the bidimensional results of irRC, but with less measurement variability. Based on these findings and in order to utilize

both the established criteria of irRC and RECIST 1.1, the two systems have been adapted, modified, and combined into the Immune-related Response Evaluation Criteria in Solid Tumors (irRECIST). The adapted irRECIST criteria are modifications to the irRC, incorporating the findings of Nishino et al. and the advantages of RECIST 1.1 while overcoming the shortcomings of each of the other guidelines.

irRECIST

Immune-related RECIST (irRECIST) guidelines according to Bohnsack et al. are presented below.

I. Baseline Assessments in irRECIST

In irRECIST, baseline assessment and measurement of measurable/non-measurable and target/non-target lesions and lymph nodes are in line with RECIST 1.1.

One new definition is added: If a subject has no measurable and no non-measurable disease at baseline the radiologist will assign 'No Disease' (irND) as the overall tumor assessment for any available follow-up time points unless new measurable lesions are identified and contribute to the total measured tumor burden (TMTB). irND is a valid assessment in studies with adjuvant setting where the protocol and study design allow the inclusion of subjects with no visible disease

Follow-up Assessments in irRECIST

A. Follow-up recording of target and new measurable lesions

The key difference in irRECIST is that the appearance of new lesions does not automatically indicate progression. Instead, all measured lesions (baseline-selected target lesions and new measurable lesions) are combined into the total measured tumor burden (TMTB) at follow up. Baseline-selected target lesions and new measurable lesions are NOT assessed separately. Measurements of those lesions are combined into the TMTB, and one combined assessment provided.

In order to be selected as new measurable lesions (≤ 2 lesions per organ, ≤ 5 lesions total, per time point), new lesions must meet criteria as defined for baseline target lesion selection and meet the same minimum size requirements of 10 mm in long diameter and minimum 15 mm in short axis for new measurable lymph nodes. New measurable lesions should be prioritized according to size, and the largest lesions elected as new measured lesions.

B. Follow-up non-target assessment

RECIST 1.1 definitions for assessment of non-target lesions apply. The response of non-target lesions primarily contributes to the overall response assessments of irCR and irNon-CR/Non-PD (irNN). Non-target lesions do not affect irPR and irSD assessments. Only a massive and unequivocal worsening of non-target lesions alone, even without progress in the TMTB is indicative of irPD. In alignment with RECIST 1.1, baseline selected non-target lesions can never convert to measurable lesions, not even if they increase in size at

subsequent time points and become measurable. Only true new lesions can be measured and contribute to the TMTB.

C. Follow-up for New Non-Measurable Lesions

All new lesions not selected as new measurable lesions are considered new non-measurable lesions and are followed qualitatively. Only a massive and unequivocal progression of new non-measurable lesions leads to an overall assessment of irPD for the time point. Persisting new non-measurable lesions prevent irCR.

Overall Assessments for irRECIST

The irRECIST overall tumor assessment is based on TMTB of measured target and new lesions, non-target lesion assessment and new non-measurable lesions.

At baseline, the sum of the longest diameters (SumD) of all target lesions (up to 2 lesions per organ, up to total 5 lesions) is measured. At each subsequent tumor assessment (TA), the SumD At each subsequent tumor assessment (TA), the SumD of the target lesions and of new, measurable lesions (up to 2 new lesions per organ, total 5 new lesions) are added together to provide the total measurable tumor burden (TMTB).

Table 14. Evaluation of Overall Assessment – irRECIST criteria

Overall Assessments by irRECIST	
Complete Response (irCR)	Complete disappearance of all measurable and non-measurable lesions. Lymph nodes must decrease to < 10 mm in short axis.
Partial Response (irPR)	
Decrease of $\geq 30\%$ in TMTB relative to baseline, non-target lesions are irNN, and no unequivocal progression of new non-measurable lesions
 
• If new measurable lesions appear in subjects with no target lesions at baseline, irPD will be assessed. That irPD time point will be considered a new baseline, and all subsequent time points will be compared to it for response assessment. irPR is possible if the TMTB of new measurable lesions decreases by $\geq 30\%$ compared to the first irPD documentation• irRECIST can be used in the adjuvant setting, in subjects with no visible disease on CT/MRI scans. The appearance of new measurable lesion(s) automatically leads to an increase in TMTB by 100% and leads to irPD. These subjects can achieve a response if the TMTB decreases at

	
follow-up, as a sign of delayed response.
 
Based on the above, sponsors may consider enrolling subjects with no measurable disease and/or no visible disease in studies with response related endpoints.
Stable Disease (irSD)	Failure to meet criteria for irCR or irPR in the absence of irPD
Progressive Disease (irPD)	
Minimum 20% increase and minimum 5 mm absolute increase in TMTB compared to nadir, or irPD for non-target or new non-measurable lesions. Confirmation of progression is recommended minimum 4 weeks after the first irPD assessment. An irPD confirmation scan may be recommended for subjects with a minimal TMTB %-increase over 20% and especially during the flare time-window of the first 12 weeks of treatment, depending on the compound efficacy expectations, to account for expected delayed response.
 
In irRECIST a substantial and unequivocal increase of non-target lesions is indicative of progression.IrPD may be assigned for a subject with multiple new non-measurable lesions if they are considered to be a sign of unequivocal massive worsening
Other	
irNE: used in exceptional cases where insufficient data exist.
 
irND: in adjuvant setting when no disease is detected
 
irNN: no target disease was identified at baseline, and at follow-up the subject fails to meet criteria for irCR or irPD

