12.2.1 Disease Parameters

Measurable disease – Measurable lesions are defined as those that can be accurately measured in at least one dimension (longest diameter to be recorded for non-nodal lesions and short axis for nodal lesions) as >20mm by chest x-ray, as >10mm with CT scan or MRI, or >10mm with calipers by clinical exam. All tumor measurements must be recorded in millimeters (or decimal fractions of centimeters).

To be considered pathologically enlarged and measurable, a lymph node must be > 15 mm in short axis when assessed by CT scan (CT scan slice thickness recommended to be no greater than 5 mm). At baseline and in follow-up, only the short axis will be measured and followed.

Note: Tumor lesions that are situated in a previously irradiated area are not considered measurable unless there is evidence of progression after radiation therapy.

Non-measurable disease – All other lesions (or sites of disease), including small lesions (longest diameter <10mm or pathological lymph nodes with ≥ 10 to <15mm short axis) are considered non-measurable disease. Bone lesions, leptomeningeal disease, ascites, pleural/pericardial effusions, lymphangitis cutis/pulmonitis, inflammatory breast disease and abdominal masses (not followed by CT or MRI), are considered as non-measurable.

Target lesions – All measurable lesions up to a maximum of 2 lesions per organ and 5 lesions in total, representative of all involved organs, should be identified as target lesions and recorded and measured at baseline. Target lesions should be selected on the basis of their size (lesions with the longest diameter), be representative of all involved organs, but in addition should be those that lend themselves to reproducible repeated measurements. A sum of the diameters (longest for non-nodal lesions, short axis for nodal lesions) for all target lesions will be calculated and reported as the baseline sum diameters. The baseline sum diameters will be used as a reference to further characterize any objective regression in the measurable dimension of the disease.

Non-target lesions – All other lesions (or sites of disease) including any measurable lesions over and above the 5 target lesions should be identified as non-target lesions and should also be recorded at baseline. Measurements of these lesions are not required, but the presence, absence or in rare cases unequivocal progression of each should be noted throughout follow-up.

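### Section 12.12 gives conflicting rules on non-target lesions for irPR and on the axis for nodes, so secondary irRECIST calls depend on which sentence is followed

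*Combined protocol and SAP*

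**What the plan says.** Section 12.1 makes irRECIST the secondary response criterion. Section 2.0 lists the 24-week best objective response rate and the 24-week PFS rate by irRECIST as secondary objectives, both for the first 20 patients and for each histology cohort.

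**Non-target lesions**

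- Section 12.12, part B: "Non-target lesions do not affect irPR and irSD assessments". The same paragraph uses irNN as the abbreviation for Non-CR/Non-PD, meaning lesions that persist without progressing.
- Table 14, irPR row: besides a TMTB fall of 30% or more, the row requires that "non-target lesions are irNN, and no unequivocal progression of new non-measurable lesions".
- Table 14, irSD row: "Failure to meet criteria for irCR or irPR in the absence of irPD".
- Table 14, Other row: "irNN: no target disease was identified at baseline, and at follow-up the subject fails to meet criteria for irCR or irPD".

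**Nodes**

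- Section 12.12, overall assessments: the baseline quantity is "the sum of the longest diameters (SumD) of all target lesions". At follow-up, new measurable lesions are added to it to give TMTB. No exception is made for nodes.
- Section 12.2.1: target lesions enter the sum as "longest for non-nodal lesions, short axis for nodal lesions", and only a node's short axis is followed.
- Section 12.12, baseline assessments: node measurement follows RECIST 1.1.
- Section 12.12 also uses short axis for the minimum size of a new node and for irCR.

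**The concern.** Two readers working in good faith from the same scans can reach different irRECIST categories. The irPR conflict also inverts the ordering: a patient whose non-target disease has disappeared can score below one whose non-target disease persists.

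The situations are foreseeable. Section 9.0 lets the injected palpable lesion serve as the target when no other suitable one exists, so some patients may have no non-target lesion. Sections 4.2 and 6.1 list nodal lesions among the injectable sites, so nodal targets are expected.

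What is at stake is the comparison of irRECIST with RECIST 1.1. It is informative only if the two differ because of the immune-response rules, and not because of a gap in a table or the choice of a node's axis.

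**Working it through.** No figure in the plan rests on these rules, so there is none to reproduce for the conflict itself. The check applies each rule literally. All lesion sizes below are illustrative assumptions.

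**A. Non-target condition**

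Inputs: irPR needs a TMTB fall of at least 30% (Table 14); irCR needs all lesions gone (Table 14); irSD is the remainder without irPD (Table 14). Take TMTB from 100 to 50 mm with no new lesions: (50 − 100)/100 = −50%.

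| Non-target status | Part B rule | Table 14 irPR row, literal |
|---|---|---|
| Persisting (Non-CR/Non-PD) | irPR | irPR |
| All disappeared | irPR | irSD |
| None at baseline | irPR | irSD |

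In the last two rows irCR fails because 50 mm of target disease remains, irPR fails because the status is not irNN, and irPD is absent. Only irSD is left.

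**B. Node axis**

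irPD needs a rise of at least 20% and at least 5 mm from nadir (Table 14).

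*Response.* A 40 mm mass plus a node of 32 × 20 mm becomes a 32 mm mass plus a node of 20 × 9 mm.

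- Short axis for the node: 40 + 20 = 60 to 32 + 9 = 41 mm; −19/60 = −31.7%, which meets the irPR size threshold.
- Longest diameter: 40 + 32 = 72 to 32 + 20 = 52 mm; −20/72 = −27.8%, irSD.

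*Progression, target node.* A stable 20 mm lesion plus a node going from 24 × 16 to 33 × 18 mm.

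- Short axis: 36 to 38 mm; +2 mm, +5.6%, not irPD.
- Longest diameter: 44 to 53 mm; +9 mm, +20.5%, irPD.

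*Progression, new node.* A 28 × 15 mm node appears on an otherwise unchanged 80 mm sum. Section 12.12 sets the minimum for a new node at 15 mm; section 12.2.1 asks for more than 15 mm, so this case sits at the edge.

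- Short axis: 15/80 = 18.8%, not irPD.
- Longest diameter: 28/80 = 35%, irPD.

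*Mixed use.* If baseline follows section 12.2.1 (16 mm) and follow-up follows the SumD wording (24 mm), an unchanged 24 × 16 mm node as sole target reads +8 mm, +50%, irPD.

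**C. Size on the endpoint**

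One reclassified patient moves ORR by 1/10 = 10 points in a histology cohort and by 1/20 = 5 points in the first group. For example, 3/10 has an exact 95% interval of 0.067 to 0.652 and 2/10 has 0.025 to 0.556. Both agree with Table 15 (0.07 to 0.65 and 0.03 to 0.56).

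The irPR/irSD conflict does not move PFS, since neither class is progression. The node conflict can.

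**The case against.** The best defence is that a sensible reader would resolve both conflicts. Most of the text points to short axis for nodes: section 12.2.1, the baseline part of section 12.12, the new-node size rule and irCR. Only the expansion of SumD says otherwise. This makes the intent fairly clear, but the SumD sentence is the operative definition of the quantity that is thresholded, so it still needs correcting. It is also fair that the lesion sizes above were chosen to straddle the cut-offs, that the endpoints are secondary and descriptive with no test attached (section 14.1), and that section 12.1 excludes irRECIST from treatment decisions.

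Four stronger readings are tempting, and the documents do not support them:

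- *The primary endpoint has the same gap, because Table 13 has no row for target PR with non-target CR or with no non-target lesions.* The row is missing, but section 12.3.1.1 defines PR on target lesions alone, and its SD requires shrinkage too small for PR. SD is not residual there, so such a patient cannot fall into it.
- *No patient with target disease can ever be irPR, because the Other row ties irNN to having no target disease at baseline.* That row lists overall assessment codes, and part B gives irNN its Non-CR/Non-PD meaning for non-target lesions. The double meaning is a defect of wording and does not bar irPR for everyone.
- *The caps on new lesions conflict.* Both are stated per assessment and agree.
- *Progression will be called on a node's long axis.* It can be if the SumD sentence is followed. The documents do not show that it has been or will be.

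**Conclusion.** Both conflicts are in the current text and should be reconciled. Under a literal reading of Table 14, a patient with a TMTB fall of 30% or more and resolved or absent non-target disease is scored irSD, which lowers irRECIST ORR. The two node rules can change irPR and irPD calls where a target or new measurable node is present, which bears on irRECIST ORR and 24-week irRECIST PFS.

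The conclusion rests on literal application of the quoted rules. The documents give no count of patients with nodal targets or with absent or resolved non-target disease, so the frequency, and hence the total effect on any reported rate, is unknown. The effect per patient is 10 points in a cohort of 10 and 5 points in 20. The primary RECIST 1.1 endpoint and its design are not affected.

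**What to change.** 1. Table 14, irPR row: replace the irNN condition with *non-target lesions are not irPD (irCR, Non-CR/Non-PD, or none present)*.
2. Table 14, Other row: state that the meaning of irNN tied to no target disease at baseline applies only as an overall assessment code.
3. Section 12.12, overall assessments: define SumD and TMTB as longest diameter for non-nodal lesions and short axis for nodal lesions, as in section 12.2.1.
4. Section 4.1 already reports response rates for the first 20 patients, and section 16.3 refers to the study as completed. Record the clarification with its date, state that it was made after response data were known, and apply it to every patient alike.

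The cost is a short amendment or a dated analysis note, plus a re-check of irRECIST calls already made. No new imaging is needed, because short axis is what section 12.2.1 already has readers record. If any node was recorded only by its long axis, its short axis would have to be read from the existing scans.

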12.13.17 Verification of Response

irRECIST response must be confirmed no less than 4 weeks from the initial irRECIST documented response.

13.0 CRITERIA FOR REMOVAL FROM STUDY

Patients will be removed from the study when any of the criteria listed below applies. The reason for removal from the study and the date the patient was removed must be documented in the EDC system.

Patients may be replaced if they come off study for reasons other than progressive disease prior to receiving their second dose of talimogene laherparepvec and/or pembrolizumab. Unless otherwise stated, patients will be included in the safety and/or efficacy analyses. Patients evaluable for efficacy analysis will include all patients treated with talimogene

laherparepvec or pembrolizumab and assessable for response. Patients who are missing an assessment of response post baseline will not be considered evaluable for response unless they missed the assessment due to progression of disease in which case they will be considered non-responders for that time point. Patients who miss an assessment of response post baseline for any reason other than progression of disease will be replaced.

In the absence of treatment delays due to adverse events, treatment with intralesional talimogene laherparepvec may continue until one of the following criteria applies:

- Disappearance of injectable lesions,
- Complete response,
- Confirmed progression of disease or clinical progression,
- Intercurrent illness that prevents further administration of treatment,
- Intolerance of study treatment,
- 35 cycles from the date of the first dose of talimogene laherparepvec and Pembrolizumab in the setting of patients with locally advanced/metastatic sarcoma. Study therapy may continue beyond 35 cycles in patients who are agreeable, deemed to be clinically benefiting from study therapy and at the discretion of the investigator. Patients who discontinue study therapy after a maximum of 35 cycles of study therapy will be allowed to resume study therapy in the setting of progression of disease off study therapy.
- After completion of up to 8 cycles of study therapy in the setting of patients with operable, recurrent sarcoma who will then proceed to surgical resection of their disease
- Patient decides to withdraw from the study
- End of study, whichever occurs first.
- Physician's decision to withdraw a patient from the study for a reason not listed
- Subject is lost to follow-up

In the absence of treatment delays due to adverse events, treatment with pembrolizumab may continue until one of the following criteria applies:

- Confirmed progression of disease or clinical progression
- Intercurrent illness that prevents further administration of treatment
- Intolerance of study treatmentCompletion of 35 treatments (approximately 2 years) with pembrolizumab
 - o Note: The number of treatments is calculated starting with the first dose. Participants who stop the combination or pembrolizumab after receiving 35 doses may be eligible for retreatment if they progress after stopping study treatment provided they meet the requirements detailed in Section 9.2.1. Participants may be retreated in the Second Course Phase (Retreatment) for up to an additional 17 cycles (approximately 1 year).
- After completion of up to eight (8) cycles of study therapy in the setting of patients with recurrent, operable sarcoma who will then proceed to surgical resection of their disease.

- On completion of surgery, these patients will be expected to complete up to 17 treatments (approximately 1 year) total (neoadjuvant and adjuvant) with pembrolizumab as tolerated -
- Patient decides to withdraw from the study,
- End of study, whichever occurs first,
- Physician's decision to withdraw a patient from the study for a reason not listed
- Subject is lost to follow-up

Subjects with a CR may stop injections of talimogene laherparepvec upon complete disappearance of injectable lesions, but treatment with pembrolizumab will be continued unless one of the criteria for treatment discontinuation is met. Study therapy may continue for a total of 35 cycles in the absence of confirmed progression of disease or clinical progression, disappearance of injectable lesions (talimogene laherparepvec only), intercurrent illness that prevents further administration of treatment, or intolerance of study treatment. Patients who discontinue study therapy after a maximum of 35 cycles of study therapy will be allowed to resume study therapy for an additional 17 cycles in the setting of progression of disease off study therapy. In the neoadjuvant setting, TVEC and pembrolizumab will continue for up to 8 cycles prior to surgical resection. On completion of surgery pembrolizumab alone will continue as tolerated for a total of 17 cycles (neoadjuvant and adjuvant therapy).

Due to the mechanism of action, subjects may experience growth in existing tumors or the appearance of new tumors prior to maximal clinical benefit of talimogene laherparepvec and pembrolizumab. The patient may be allowed to continue study treatment after initial RECIST 1.1 defined progression if they are assessed by the treating physician to be deriving clinical benefit and tolerating study treatment. The treating physician may consult with the overall study PI for help with assessing the patient. Such patients should discontinue study therapy upon further evidence of progression.

Safety follows up and End of Study visit

Upon permanent discontinuation from the study treatment for any reason, the following procedures will be performed approximately 30 (+7) days after the last dose of talimogene laherparepvec or the last dose of pembrolizumab, whichever is later in patients with metastatic or locally advanced sarcoma.

- Full medical history, physical exam, assessment of performance status by KPS or ECOG status
- Review of concomitant medications
- Complete vital signs (pulse, blood pressure, temperature, respiratory rate) as well as weight and height. Height may be documented at any time prior to registration.
- 12-lead electrocardiogram (EKG)
- Serum β -HCG pregnancy test for women with child-bearing potential. Complete blood count with differential, including lymphocyte and eosinophil count.

- Comprehensive metabolic panel (glucose, blood urea nitrogen, creatinine, sodium, potassium, chloride, bicarbonate, calcium, total protein, albumin, serum bilirubin, alkaline phosphatase, ASL, AST, phosphorus, magnesium, TSH, T4 free).
- Amylase and lipase
- An optional biopsy will be offered at progression of disease.

Patients whose treatment is interrupted or permanently discontinued due to an adverse event or clinically significant laboratory value must be followed until resolution or stabilization of the event.

Reporting of adverse events will occur for up to 30 days for serious adverse events (within 30 [+7] days after the last administration of talimogene laherparepvec or pembrolizumab, whichever is later), Events of Clinical Interest (within 30 [+7] days after the last administration of talimogene laherparepvec or pembrolizumab, whichever is later), and documentation of concomitant medications. In the neoadjuvant cohort, reporting of serious adverse events will occur for up to 30 days from the date of surgical resection.

Long-Term Follow-up Procedures:

All subjects who permanently discontinue study drug for any reason other than withdrawal of full consent will be contacted by clinic visit or telephone to assess survival and initiation of additional sarcoma therapy. Contact for all subjects will be attempted every 12 weeks (\pm 14 days) following the safety follow-up visit until death, subject withdraws full consent, or up to 12 months after the end of treatment for patients with metastatic or locally advanced sarcoma and for up to 36 months after the completion of surgery for recurrent, operable sarcoma. If patients do not proceed to surgical resection upon conclusion of study therapy, patients will be followed with interval scanning and clinical surveillance every 6-8 weeks for one year or until completion of participation on study.

